#### **4.1.4 Definitions of Visit Windows**

Time windows are defined for all summaries of vital signs, laboratory data, PRO around visits in Section 4.1.4.1 and for tumour assessments around the scheduled RECIST assessment time in Section 4.1.4.2

##### **4.1.4.1 Visit Windows for Safety and PRO Assessments**

The following conventions will apply for safety and PRO data:

- The time windows should be exhaustive so that data recorded at any time point has the potential to be summarized. Inclusion within the time window should be based on the actual date and not the intended date of the visit.
- All unscheduled visit data will have the potential to be included in the summaries.
- The window for the visits following baseline will be constructed in such a way that the upper limit of the interval falls half way between the two visits (the lower limit of the first

post-baseline visit will be Day 2). If an even number of days exists between two consecutive visits, then the upper limit will be taken as the midpoint value minus 1 day.

For example, the visit windows for vital signs data are:

- Week 1; nominal day 1, visit window Day 1
- Week 4; nominal day 29, visit window 2 – 42
- Week 8; nominal day 57, visit window 43 – 70
- Week 12; nominal day 85, visit window 71 – 98
- Week 16; nominal day 113, visit window 99 – 126
- Visits after treatment discontinuation will be assigned to the last treatment cycle for up to 15 days only. Visits after the 15 days will contribute to the following 30 days post treatment discontinuation interval, see below.
- Visits up to 90 days after last dose will be assigned similarly to the definition for the visits under treatment, but for 30 day intervals after treatment discontinuation, eg,:
  - 30 days after last dose, visit window 16 – 45
  - 60 days after last dose, visit window 46 – 75
  - 90 days after last dose, visit window 76 – 97
  - Data recorded after 97 days after last dose will not contribute to the analysis period of up to 90 days following the date of last dose, and will not be re-mapped
- For summaries showing the maximum or minimum values, the maximum/minimum value recorded on treatment will be used (regardless of where it falls in an interval).
- Listings should display all values contributing to a time point for a patient.

For visit based summaries:

- If there is more than one value per patient within a time window then the closest value to the scheduled visit date should be used, or the earlier in the event the values are equidistant from the nominal visit date. If there are two values recorded on the same day and the parameter is CTCAE gradable then the record with the highest toxicity grade should be used. The listings should highlight the value for that patient that went into the summary table, wherever feasible. Note: in summaries of extreme values all on-treatment values collected are used including those collected at unscheduled visits.
- For summaries at a patient level, all values should be included, regardless of whether they appear in a corresponding visit-based summary, when deriving a patient level statistic such as a maximum.

#### **4.1.4.2 Visit Windows for Tumour Assessments**

The following conventions will apply for tumour assessment data:

- All tumour assessments available during the study should be used for the efficacy analysis. A windowing rule will be applied and will follow the CSP allowed visit window; therefore, any RECIST assessment performed within  $\pm 1$  week of the CSP scheduled visit will be used for that visit.
- If there are any assessments outside these visit windows, they will also be included in the closest visit window following the intent-to-treat principle. The tumour assessments which are outside the visit windows will be flagged in the data listings.

The above could result in more than one tumour assessments within a window and in that case, the one closest to the scheduled assessment will be used.

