4.2.2 Rationale for study efficacy endpoints

The secondary aim of this study is to determine the efficacy of durvalumab (MEDI4736) 1500 mg q4w in terms of PFS and OS. PFS has been found to be correlated with OS in previous CRT studies (Mauguen et al 2013). Although the OS benefit has exceeded the PFS benefit in other studies of immune checkpoint inhibitors in advanced-stage NSCLC (Borghaei et al 2015), there are certain settings in which the utility of survival as an endpoint may potentially be confounded by subsequent therapies. Specifically, there are currently a number of molecules targeting the PD-1/PD-L1 pathway in late-stage development for the treatment of first-, second-, and/or third-line metastatic NSCLC. It is anticipated that these agents may be approved or become available for use through expanded-access mechanisms or additional clinical studies while the PACIFIC 6 Study is ongoing. This poses challenges in being able to fully characterize effects on OS if patients subsequently receive these immunotherapeutic agents.

Anti-tumour activity will be assessed according to RECIST 1.1 guidelines, with the understanding that in the context of post-radiation changes, tumour assessment may be difficult and may need to be repeated over time to reach a clear determination regarding responses and PD (see Section 8.1). The tumour-based efficacy analyses will be conducted by programmatically deriving each efficacy endpoint based on RECIST 1.1 criteria. PFS will be programmatically derived from Investigators' tumour data from all scans based upon RECIST 1.1.

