### 3.3 Efficacy Variables

All RECIST assessments, whether scheduled or unscheduled, and regardless of whether a patient discontinues durvalumab treatment or receives another anti-cancer therapy will be included in the calculation of efficacy variables.

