  - All laboratory data, vital signs data that are recorded at unscheduled visits will be included in the summaries using the visit windows defined in Section [4.1.4.1](#).
  - The tumour measurements and PRO data should not be affected by any delays in treatment cycles/dates of start of treatment cycles as it is intended that they are only recorded at pre-scheduled time points. These data will be included in the summaries and analyses of the data using the visit windows defined in Section [4.1.4.2](#).
- All data collected including scheduled, delayed and unscheduled data will be listed in the patient data listings which are produced for all treated patients. They will be ordered by treatment/not treated, centre, WHO/ECOG PS group, patient and visit and, if relevant, timepoint when they were recorded. Patients who are included in the SAF will be flagged. Depending on the availability of the data, all data for the patients who are not treated will be listed separately. They will be ordered by centre, WHO/ECOG PS group, patient and visit and timepoint, if relevant.

- All adverse events will be coded using MedDRA and NCI CTCAE Grade and will be reported using SOC and PT, NCI CTCAE Grade, as appropriate.
- All concomitant and previous medications will be coded using WHO drug dictionary and will be reported using anatomical therapeutic chemical (ATC) classification and generic term.
- Baseline is defined as the last assessment of the variable under consideration prior to the first dose of durvalumab regardless of whether the assessment is on Day 1, Screening or unscheduled.

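### SAP 4.1.4.2 keeps one tumour scan per visit window, contradicting the all-scans rule in SAP 3.3 and protocol 4.2.2; applied before endpoint derivation, it could drop an unscheduled progression scan

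*SAP*

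**What the plan says.** SAP 4.1.4.2 begins: "All tumour assessments available during the study should be used for the efficacy analysis". It sets windows of one week either side of each scheduled scan and says of scans outside them that "they will also be included in the closest visit window following the intent-to-treat principle". It ends by resolving collisions: where a window holds more than one scan, "the one closest to the scheduled assessment will be used". It gives no priority to a scan showing progression and no rule for ties.

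SAP 4.1.1 sets the scope. Of the tumour and PRO data it says "These data will be included in the summaries and analyses of the data using the visit windows defined in Section" 4.1.4.2. SAP 3.1 adds that PFS, ORR and the other RECIST outcomes are calculated from the overall visit responses.

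Other text points the opposite way. SAP 3.3 counts "All RECIST assessments, whether scheduled or unscheduled" in the calculation of efficacy variables. Protocol 4.2.2 derives PFS from the investigators' "tumour data from all scans based upon RECIST 1.1".

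**The concern.** A scan that is not used cannot be one of all the scans used, so SAP 4.1.4.2 conflicts with its own first sentence, with SAP 3.3 and with protocol 4.2.2. Two competent programmers could follow the SAP and produce different PFS results from the same data.

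The selection rule is not confined to by-visit tables. SAP 4.1.1 extends the windows to analyses, and 4.1.4.2 introduces them in the same bullet as the efficacy analysis. The neighbouring section on safety and PRO windows, 4.1.4.1, does limit its closest-value rule to visit-based summaries, protects patient-level derivations and gives a tie rule. The tumour section does none of these.

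At stake are the dates of progression. If an unscheduled scan showing progression is set aside in favour of an on-schedule scan without progression, the event is dated later or disappears. DoR takes its end date from PFS (SAP 3.3.5), so it is affected too. The study has a single arm and is meant to complement PACIFIC (SAP section 1), so no concurrent control would share the shift.

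**Working it through.** No sample size, power or event count in the plan depends on this rule, so there is no figure to reproduce for it. The SAP's own schedule arithmetic in 3.3.1 was checked first: week 39 is 39 × 7 + 1 = Day 274, week 49 is 49 × 7 + 1 = Day 344, and the two-missed-visit gaps of 17, 18, 22 and 26 weeks are right.

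**Inputs.** Scans are 8-weekly and later 12-weekly (SAP 3.3.1). The 8-weekly visits fall on Days 57, 113, 169 and so on. An off-window scan joins the nearest visit, and the scan closest to schedule is kept (SAP 4.1.4.2). Without a recorded progression or death, PFS is censored at the last evaluable assessment (SAP 3.3.1).

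**One patient.** The Week 16 scan on Day 113 shows stable disease. An unscheduled scan on Day 134 shows progression.
- Distance to Week 16: 134 − 113 = 21 days. Distance to Week 24: 169 − 134 = 35 days.
- The Day 134 scan joins the Week 16 window and loses to the Day 113 scan, which is on schedule.
- If the Week 24 scan shows progression, the event moves to Day 169, a delay of 169 − 134 = 35 days.
- If there is no later scan or death, the event is lost and the patient is censored at Day 113.
- Using all scans, progression is dated Day 134.

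**Range of delay.** Take an earlier scan on time without progression, an unscheduled progression scan *d* days later, and the next scheduled scan on time and showing progression. In an interval of *L* days the unscheduled scan joins the earlier window if *d* < *L* − *d*, and the delay is *L* − *d*.
- 8-weekly, *L* = 56: *d* runs from 1 to 27, so the delay is 55 down to 29 days. This covers 27 of the 55 dates between scans.
- 12-weekly, *L* = 84: *d* runs from 1 to 41, so the delay is 83 down to 43 days. This covers 41 of the 83 dates.
- At exactly *d* = 28 or 42 the scan is equidistant from two visits, and no rule applies.

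This count covers only collisions with the earlier scan. A progression scan in the second half of an interval joins the next window. It is displaced only if the next scheduled scan is also taken, and the delay is then at most 27 or 41 days.

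**Effect on the estimate.** Kaplan-Meier PFS was simulated for 40,000 patients with exponential times, using all scans and then the closest scan per window. These inputs are assumptions: median PFS of 8, 11 or 16.8 months (8 and 16.8 are quoted in the protocol Introduction for CRT alone and for PACIFIC; 11 is an intermediate value); 10% to 40% of progressions first seen on an unscheduled scan; first 12-weekly scan at week 60; only first-half collisions; deaths ignored.

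| Later scan shows progression in | Rise in PFS12 (points) | Rise in PFS24 (points) |
|---|---|---|
| all discarded cases | 0.2 to 1.1 | 0.2 to 0.9 |
| no discarded cases | about 1.4 to 7 | 1.4 to 7.5 |

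**The case against.** The strongest reply is that the endpoint definitions already settle the matter. SAP 3.3 is explicit. PFS and DoR in 3.3.1 and 3.3.5 are built on assessment dates, two missed visits are counted as elapsed weeks and not as empty windows, and none of these definitions refers to 4.1.4.2. The reference in 4.1.1 is loosely drafted: it also sends PRO data to 4.1.4.2, although PRO windows are in 4.1.4.1. On this reading the closest-scan sentence is a display rule that was not labelled as one.

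This has force. It shows which reading was probably intended, and it makes any bias conditional. It does not remove the conflict, because 4.1.1 and 4.1.4.2 still direct the selection into the analysis and nothing in 3.3 says which instruction prevails.

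Other limits also stand. A progression scan alone in its window is kept. Protocol 7.1.1 asks for a follow-up scan after progression no later than the next scheduled visit, and death is a PFS event, so a lost event is not the planned course. A dropped unscheduled response scan could act the other way, by delaying the start of response (shorter DoR) or removing a confirmation (lower ORR). The endpoints are secondary, no hypothesis is tested (protocol 9.1), and the primary safety endpoint is untouched. For scale, at an assumed PFS12 of 50% in 150 patients without censoring, the 95% half-width is 1.96 × √(0.25/150) = 8 points.

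**Conclusion.** The contradiction is in the current text and should be removed. Its effect is conditional: it arises only if scans are selected by window before the endpoints are derived, and only where another scan in the same window is closer to schedule. Under those conditions, dropping a progression scan can delay or remove an event but cannot advance one. The Kaplan-Meier PFS estimate and the DoR end date therefore shift upward. For first-half scans the delay per affected patient is about 29 to 55 days (8-weekly) or 43 to 83 days (12-weekly). The effect on PFS12 is around a point or less if later scans pick up the progression, and larger if they do not. These sizes rest on assumed rates, because the documents give no frequency for unscheduled scans.

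A reader might infer more: that the plan will lengthen PFS and DoR, that the discarded scans will mostly be the progression scans, or that BoR will improve. The documents do not support this. SAP 3.3 argues against applying the selection to endpoints, and nothing says why unscheduled scans are taken. In the worked example the Day 113 scan already shows stable disease, so a best response of stable disease is unchanged. The net direction for DoR and ORR is not determined either, since response scans can be dropped too.

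**What to change.** - In SAP 4.1.4.2, state that the visit windows and the closest-scan rule apply only to by-visit displays, and add a rule for scans equidistant from the scheduled date or from two visits.
- State that PFS, BoR, ORR and DoR are derived from every scan at its actual date, with the first RECIST 1.1 progression on any scan as the progression date. Keep the existing subsequent-therapy exclusions and missed-visit censoring. This also agrees with protocol Appendix F, under which a first progression is not revised if the next scan fails to confirm it.
- In SAP 4.1.1, amend the cross-reference so that the tumour windows govern by-visit summaries only, and point PRO data to 4.1.4.1.

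The cost is a few sentences in the SAP. No new data are needed, and the change carries out what SAP 3.3 and protocol 4.2.2 already say.

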## 4.2 Study Population

### 4.2.1 Patient Disposition

The following patient disposition summaries will be produced:

- The number and percentage of patients who were screened, who were screening failures, and who received and did not receive durvalumab will be summarised for all patients.
- Discontinuation from durvalumab and/or discontinuation from study, together with reason for discontinuation (including the reason due to COVID-19 Pandemic) will be summarised using the SAF.
- Disruptions due to COVID-19
- Summary of confirmed/suspected COVID-19 infection.

The date of the last contact (date of withdrew consent/lost to follow-up/died) will be listed in patient disposition listings. COVID-19 study disruptions will also be listed as recorded as protocol deviations, which were assessed as COVID-19 related.

### 4.2.2 Protocol deviations

Important protocol deviations are defined in Section 2.2 and will be listed and summarized for the SAF, including a summary of those identified as resulting from the COVID-19 pandemic.

The number and percentage of patients with any IPD will be summarized for each IPD category. Patients with more than one deviation in the same IPD category will be counted once for that IPD category. Any patients who have deviations in more than one IPD category will be counted once in the overall summary. The number of patients with at least 1 COVID-19 related important protocol deviation and the number of patients with at least 1 important protocol deviation, excluding COVID-19 will be presented by IPD category.

### 4.2.3 Demography and Baseline Characteristics

Demographic and other baseline characteristics (see Section 3.5.1) will be listed for all patients and summarised for the SAF, as:

- Demographics (age, age group [ $<50$ ,  $\geq 50$ - $< 65$ ,  $\geq 65$ - $<75$ , and  $\geq 75$  years], sex, race and

ethnicity)

- Demographic characteristics in patients with confirmed/suspected COVID-19 infection.
- Patient characteristics at baseline (height, weight [prior to start of sCRT, and after sCRT at screening, and the change], weight groups [ $<40$ ,  $\geq 40$ - $<75$ ,  $\geq 75$ - $<90$ ,  $\geq 90$ - $<120$ , and  $\geq 120$  kg], body mass index (BMI) after sCRT, and BMI groups [Underweight ( $<18.5$ ), Normal weight ( $=18.5$  -  $<25.0$ ), Overweight ( $=25.0$  -  $<30.0$ ), Obese ( $=30.0$ )]
- Nicotine use and consumption
- A summary and a list of patients by site and country will be provided.
- Previous disease-related sequential chemoradiotherapy
  - Sequential, no chemotherapy overlap with radiotherapy
  - Sequential, 1 cycle chemotherapy overlap with radiotherapy
  - Concurrent,  $>1$  cycle chemotherapy overlap with radiotherapy

The number of cycles used for the classification will be derived by the number of days from the overlapping time interval from each specific chemotherapy regimen overlapping with radiotherapy, divided by 21 days, and rounded up to the next integer, and will subsequently be summed up by patient.

- Previous treatments for early stage disease

Medical history and relevant surgical history are coded using MedDRA and will be summarized by SOC and PT. Medical history will also be summarized for patients with confirmed/suspected COVID-19 infection.

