5.1 Inclusion criteria

For inclusion in the study, patients should fulfil the following criteria:

Informed consent

- 1 Capable of giving signed informed consent, which includes compliance with the requirements and restrictions listed in the ICF and in this protocol.
- 2 Provision of signed and dated, written ICF prior to any mandatory study specific procedures, sampling, and analyses.
- 3 Provision of signed and dated written genetic informed consent prior to collection of sample for genetic analysis (optional).

The ICF process is described in [Appendix A, A 3](#).

Age

- 4 18 years or older at the time of signing the ICF.

Type of patient and disease characteristics

- 5 Histologically- or cytologically-documented NSCLC with locally-advanced, unresectable Stage III disease (according to the IASLC Staging Manual Version 8 [[IASLC 2016](#)]). Positron emission tomography (PET)/CT, MRI of the brain, and endobronchial ultrasound with biopsy are highly encouraged at diagnosis.

- 6 Receipt of sCRT which must have been completed within 42 days prior to first IP dose administration in the study.
 - (a) The platinum-based chemotherapy regimen must contain cisplatin or carboplatin and 1 of the following agents: etoposide, vinblastine, vinorelbine, a taxane (paclitaxel or docetaxel), or pemetrexed, according to the local SoC regimens. Platinum-based chemotherapy containing cisplatin or carboplatin and gemcitabine is permitted under certain conditions – refer to bullet point 6(b).
 - (b) Patients must have received at least 2 cycles of platinum-based chemotherapy before radiation therapy. The interval between administration of the last dose of chemotherapy regimen and start of radiation therapy must be no more than 6 weeks. Consolidation chemotherapy after radiation is not permitted.
 - (i) If the patient's platinum-based chemotherapy contained gemcitabine, no overlap between chemotherapy and radiation therapy is permitted.
 - (ii) If the patient's platinum-based chemotherapy contained any of the agents listed in 6(a) other than gemcitabine, an overlap of 1 cycle of chemotherapy and radiation therapy is acceptable.
 - (c) Patients must have received a total dose of radiation of 60 Gy \pm 10% (54 Gy to 66 Gy). Sites are encouraged to adhere to mean organ radiation dosing as follows:
 - (i) Mean lung dose <20 Gy and/or V20 <35%;
 - (ii) Mean oesophagus <34 Gy;

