- 10 Active infection including **tuberculosis** (clinical evaluation that includes clinical history, physical examination and radiographic findings, and tuberculosis testing in line with local practice), **hepatitis B** (known positive hepatitis B surface antigen [HbsAg] result), **hepatitis C virus (HCV)**, or **human immunodeficiency virus (HIV)** (positive HIV 1/2 antibodies). Patients with a past or resolved hepatitis B virus (HBV) infection (defined as the presence of hepatitis B core antibody [anti-HBc] and absence of HbsAg) are eligible.

Patients positive for hepatitis C antibody are eligible only if polymerase chain reaction is negative for HCV ribonucleic acid (RNA).

- 11 Any unresolved toxicity of NCI CTCAE Grade ≥ 2 from previous anticancer therapy with the exception of alopecia, vitiligo, and the laboratory values defined in the inclusion criteria.
 - (a) Patients with Grade ≥ 2 neuropathy or Grade ≥ 2 lymphopenia will be evaluated on a case-by-case basis after consultation with the Study Physician.
 - (b) Patients with irreversible toxicity not reasonably expected to be exacerbated by treatment with durvalumab (MEDI4736) may be included only after consultation with the Study Physician.
- 12 Known allergy or hypersensitivity to durvalumab (MEDI4736) or any of the IP excipients.

Prior/concomitant therapy

- 13 Patients who have received cCRT for locally-advanced NSCLC, or who received sCRT with at least 2 concomitant CRT cycles. Prior surgical resection (ie, Stage I or II) is permitted.

Note: Patients whose platinum-based chemotherapy contained gemcitabine and who received sCRT with at least 1 concomitant CRT cycle are excluded from this study.
- 14 Receipt of live attenuated vaccine within 30 days prior to the first dose of IP.

Note: Patients, if enrolled, should not receive live vaccine while receiving IP and up to 30 days after the last dose of IP.
- 15 Major surgical procedure (as defined by the Investigator) within 28 days prior to the first dose of IP.

Note: Local surgery of isolated lesions for palliative intent is acceptable.
- 16 Prior exposure to immune-mediated therapy, including but not limited to, other anti-CTLA-4, anti-PD-1, anti-PD-L1, and anti-PD-L2 antibodies, excluding therapeutic anticancer vaccines.
- 17 Current or prior use of immunosuppressive medication within 14 days before the first dose of IP. The following are exceptions to this criterion:

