### **2.2.2 Monitoring of Important Protocol Deviations**

Programmable PDs will be detected from the data recorded in the clinical database and will be reviewed at regular PD review meetings. At this meeting, the programmatically-derived PDs will be checked to ensure that they have been correctly classified as major or minor PDs.

On an ongoing basis throughout the study, monitoring notes or summaries will also be reviewed to determine any important post-entry deviations that are not identifiable via programming.

If the number of deviations which are considered to have the potential to impact the primary analysis is considered important, sensitivity analyses may be performed on subgroups. This will be decided during the data review meeting and before the database lock.

The final classification of IPDs will be made prior to database lock or data cut-off (DCO) for final analysis. Any other deviations from monitoring notes or reports will be reported in an appendix to the CSR.

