## 3.5 Other Variables

### 3.5.1 Baseline Characteristics

Baseline characteristics that will be collected or derived are:

- Demographics: age (years), sex, race and ethnicity.
- Patient characteristics: weight, height, body mass index (BMI).
- Medical history: name of past and/or concomitant diseases (verbatim and coded using the latest or current version of the MedDRA dictionary), start and stop dates.
- Nicotine use: smoking status (current, former, never) and pack years.
- Characteristics of NSCLC at diagnosis: original diagnosis date, primary tumour location, histology type, TNM classification, American Joint Committee on Cancer (AJCC) staging.
- Extent of disease at entry of study: current AJCC staging, evidence of disease (yes/no), sites of locally advanced disease, recent progression (yes/no, date).
- Previous disease-related sequential chemoradiotherapy: Total dose, Radiotherapy treated location, Time from completion of radiotherapy to study treatment, Type of previous chemoradiotherapy, best response to previous chemoradiotherapy, Chemotherapy Class,

Chemotherapy regimen used for sequential chemoradiotherapy, Number of chemotherapy cycles.

- Previous treatments for early stage disease (prior to definitive CRT): Radiotherapy treated location, Treatment status, Chemotherapy regimen used for early stage disease prior to CRT.
- Relevant surgical history: surgical procedure (verbatim and coded using the latest or current version of the MedDRA dictionary) and date of surgery.

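### The SAP counts overlapping chemotherapy cycles as overlap days divided by a fixed 21, which can put patients in the wrong sequential or concurrent row of the baseline table

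*SAP*

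**What the plan says.** The baseline summary in SAP 4.2.3 has three rows for prior chemoradiotherapy: sequential with no overlap; "Sequential, 1 cycle chemotherapy overlap with radiotherapy"; and concurrent, for more than one "cycle chemotherapy overlap with radiotherapy". The count behind the rows starts from the number of "days from the overlapping time interval from each specific chemotherapy regimen overlapping with radiotherapy". That number is "divided by 21 days, and rounded up to the next integer, and will subsequently be summed up by patient".

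The protocol counts cycles. For regimens without gemcitabine, inclusion 6(b)(ii) says "an overlap of 1 cycle of chemotherapy and radiation therapy is acceptable"; with gemcitabine, 6(b)(i) allows none. Exclusion 13 removes patients "who received sCRT with at least 2 concomitant CRT cycles". Inclusion 6(a) lets the regimen follow local standard of care, and neither document states a cycle length for it.

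Two other SAP sections bear on the point. Section 3.5.1 lists among the baseline data the type of previous chemoradiotherapy and "Chemotherapy regimen used for sequential chemoradiotherapy, Number of chemotherapy cycles". Section 2.2.1 makes inclusion 6 and exclusion 13 key entry criteria whose breach is an important deviation, and section 2.2.2 says "Programmable PDs will be detected from the data recorded in the clinical database".

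**The concern.** The table rows are worded in cycles, but the derivation measures calendar time. Days of overlap do not fix the number of cycles unless every regimen has 21-day cycles given on schedule. Rounding each regimen up before summing adds a second source of error, always upwards.

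The trial is meant to describe durvalumab after sequential chemoradiation, as a complement to the PACIFIC study of patients treated after concurrent chemoradiation. Sequential or concurrent is therefore the defining feature of prior treatment. A spurious count in the concurrent row would suggest breaches of exclusion 13 that did not happen. The opposite error would hide real ones. Either could also leave the baseline table at odds with the deviation listing in the same report.

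**Working it through.** The documents give no worked example or count for this rule, so there is no figure to reproduce. The check applies the rule to overlaps whose true cycle count is known.

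**Rule (SAP 4.2.3).** Count = sum over regimens of ceil(overlap days / 21). A count of 0 or 1 is sequential; more than 1 is concurrent.

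**Comparator.** The number of cycles with at least one dose given during radiotherapy. The protocol does not define an overlapping cycle, so this is an assumption.

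**Cycle length.** Not stated. Lengths of 7, 14, 21 and 28 days were tried as an assumed range.

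| Case | Overlap days | SAP count | Cycles dosed in radiotherapy | Label right? |
|---|---|---|---|---|
| One 21-day cycle | 1 to 21 | 1 | 1 | Yes, for all 21 lengths |
| Two full 21-day cycles | 42 | 42/21 = 2 | 2 | Yes |
| One 28-day cycle | 22 to 28 | ceil(22/21) = ceil(28/21) = 2 | 1 | No, for 7 of 28 lengths |
| 21-day regimen, one dose delayed to radiotherapy day 26 | 26 | ceil(26/21) = 2 | 1 | No |
| Regimen changed within one cycle | 5 and 10 | 1 + 1 = 2 | 1 | No |
| Two 7-day cycles | 14 | ceil(14/21) = 1 | 2 | No |

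Notes on the cases:

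- **28-day cycle.** The result does not need overlap to run to the end of the cycle. Take the stop date as the last dose, dosing on day 1 only, and radiotherapy starting on day s of the preceding cycle. The next dose is on day 29, so overlap is 29 − s + 1 = 30 − s days. For s = 2 to 8 this is 28 down to 22 days: count 2, with one cycle dosed during radiotherapy.
- **Delayed dose.** Suppose the last dose before radiotherapy is 2 days before it starts. Radiotherapy day 1 is then day 3 of that cycle, the next dose is due on cycle day 22 (radiotherapy day 20), and a dose on radiotherapy day 26 is 6 days late. On time the count is ceil(20/21) = 1; delayed it is 2. This assumes one start and stop date per regimen, with the stop date at the last dose.
- **Regimen change.** Summing first gives ceil(15/21) = 1. The second unit comes only from rounding each regimen separately.

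**Undefined conventions.** The SAP does not say whether the day count is inclusive, or whether a regimen stops at its last dose or at the end of its last cycle. Doses on radiotherapy days 1 and 22 give 21 days as a date difference (count 1) but 22 days inclusively (count 2). If radiotherapy starts on day 8 of one 21-day cycle, with a dose that day, and the last dose is on day 1 of the next, overlap to the last dose is 22 − 8 + 1 = 15 days (count 1). If it is run to cycle end and radiotherapy lasts that long, it is 42 − 8 + 1 = 35 days (count 2).

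**The case against.** The strongest case against is that the rule is a workable approximation for one descriptive row. For a 21-day regimen recorded once, none of the 21 possible overlap lengths within one cycle is mislabelled. The errors need conditions that the documents neither state nor exclude. Examples can also be built by changing the stop-date convention from one to the next. The delayed-dose case is arguable, since a cycle begun 2 days before radiotherapy runs into it, and someone counting cycle windows would call that two. SAP time-to-event formulas add 1 day, which suggests inclusive counting and gives the right answer for doses on days 1 and 22. Type of previous chemoradiotherapy and number of cycles are also baseline data, so a cross-check is possible.

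Most of this stands, and it limits the point to what the rule can do. It does not remove the point. The 28-day case holds with the stop date at the last dose, and the short-cycle case holds under either stop-date convention.

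A reader might infer three stronger things that the documents do not support:

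- **Every doublet patient with one overlapping cycle becomes concurrent**, because two agents give 1 + 1 = 2. The SAP works per regimen, and protocol 6(a) uses that word for the platinum and its partner together. This would need agents to be treated as separate regimens, which the wording does not suggest.
- **The count of exclusion 13 deviations is wrong.** SAP 2.2.2 does not say that the deviation check uses this rule, and it has programmed deviations checked at review meetings.
- **The main results are affected.** The safety analysis set is every patient dosed, and the primary endpoint does not use this label.

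**Conclusion.** The concern holds in a limited form. SAP 4.2.3 derives a cycle count from days, with a fixed divisor that has no stated basis, while the protocol counts cycles and sets no cycle length. The rule is right for an undelayed 21-day regimen recorded once, apart from boundary cases that turn on conventions the SAP leaves open. It can overcount with cycles longer than 21 days, a delayed dose or a regimen change, and undercount with cycles shorter than 21 days.

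The size is unknown: the documents do not give the number of patients with overlap, their regimens or their cycle lengths. The consequence is confined to the baseline description of prior therapy. The conclusion assumes that a cycle counts as overlapping when a dose of it is given during radiotherapy, and that local practice may include cycles other than 21 days. It is worth correcting because the label describes the trial's defining prior exposure and the change is small.

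**What to change.** In SAP 4.2.3, replace the rule with a count of chemotherapy cycles in which at least one dose was given from the first to the last radiotherapy fraction, inclusive, counting a doublet once. The test should be any dose, not only day 1 of the cycle. Otherwise a later dose of a cycle begun before radiotherapy would be missed, including a gemcitabine dose where no overlap is allowed.

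Where dose or cycle dates are not in the eCRF (SAP 3.5.1 does not show that they are), divide overlap days by the patient's own cycle length, taken from regimen start and stop dates and the recorded number of cycles. Sum before rounding up, and define the stop date and the day count. This gives 28/28 = 1, 14/7 = 2 and, for the regimen change, 5/21 + 10/21 = 15/21, which rounds up to 1. It does not settle every delayed dose. With two cycles before radiotherapy at a 21-day interval and the third dose 27 days after the second, the mean interval is (21 + 27)/2 = 24 days, and 26/24 still rounds up to 2. Patients near the boundary between 1 and 2 cycles therefore need individual review.

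Reconcile the result with the recorded type of previous chemoradiotherapy and with the inclusion 6(b) and exclusion 13 deviations. The cost is a revised SAP paragraph, one derivation and a short review of patients with overlap.
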